7.5.3. Unexpected Adverse Events

The IB contains the Reference Safety Information (RSI), which will be used for assessing expectedness. If an event is not listed in the RSI, it should be considered unexpected or if the AE occurs at a greater severity, specificity, or frequency, it should be considered unexpected.

7.5.4. Eliciting Adverse Event Information

The investigator is to report all directly observed AEs and all AEs spontaneously reported by the study subject/parent(s)/legal guardian/legally acceptable representative. In addition, each study subject/parent(s)/legal guardian/legally acceptable representative will be questioned about AEs at each scheduled clinic visit after study drug administration or during any telephone contact with the subject/parent(s)/legal guardian/legally acceptable representative. The type of question asked should be open-ended, for example, "*How have you been feeling?*" or a similar type of query.

7.5.5. Recording Nonserious AEs and SAEs

All AEs (both serious and nonserious) that occur in subjects during the AE reporting period must be recorded, whether or not the event is considered drug-related. In addition, any known untoward event that occurs subsequent to the AE reporting period that the investigator assesses as possibly related to the investigational drug/product should also be recorded as an AE.

All AEs are to be recorded in the source documents and on the eCRF using concise medical terminology; whenever possible, terms contained in the Medical Dictionary for Regulatory Activities should be employed. In addition, the following information should be recorded:

- Indication of whether the event is serious or nonserious (see Section 7.5.2)
- Relationship to study drug (see Section 7.5.6)
- Severity of the event (see Section 7.5.7)
- Onset date
- Resolution date, or date of death
- Action taken
- Outcome of the event

Classification of the event as serious or nonserious determines the reporting procedures to be followed.

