2.2.4.1. Clinical Variables

- All AEs
- Drug-related SAEs
- Drug-related AEs

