7.1.4. Post Treatment Follow-up Phase

The follow-up contact will be by telephone and should be completed 30 days (± 7 days) post last study drug administration or termination visit, whichever is later. Adverse events and SAEs whether or not deemed study drug-related will be followed until resolution or until they have normalized. At the investigator's discretion an office visit and additional tests may be conducted in order to ensure proper follow-up of an AE/SAE. Subjects will be closely monitored for possible rebound effects following discontinuation of study drug. Additionally, subjects who are WOCBP will be required to perform an at-home pregnancy test (study-provided) 30 days after the last dose of study drug and self-report the results via telephone.

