7.5.2. Definition of Serious Adverse Events

An SAE is an untoward medical occurrence or effect associated with the use of a study drug at any dose, regardless of whether it is considered to be related to the study drug, which results in one of the following:

- Results in death. This includes all deaths on treatment or within 30 days after last study drug administration, including deaths due to disease progression. Any death occurring later than 30 days following the last dose need not be reported as an SAE unless it is a result of an event that started within the period covered by the on-study definition. The reported AE should be the event that caused the death. In addition, any AE resulting in death that occurs subsequent to the AE reporting period and that the investigator assesses as possibly related to the study drug should also be reported as serious.
- Is life-threatening. This refers to an event in which the subject was at risk of death at the time of the event. It does not include an event that, had it occurred in a more severe form, hypothetically might have caused death.
- Requires hospitalization or prolongation of existing hospitalization (excluding hospitalizations for administration of the study drug, procedures required by the study protocol, or treatment-related diagnostic procedures; other planned hospitalizations; or hospitalizations related only to progression of disease).

Medical and scientific judgment should be exercised in deciding whether expedited reporting is appropriate in other situations, such as important medical events that may not be immediately life-threatening or result in death or hospitalization but may jeopardize the subject or may require intervention to prevent one of the other outcomes listed in the definition above. These should also usually be considered serious. Examples of such events are intensive treatment in an emergency room or at home for allergic bronchospasm; blood dyscrasias or convulsions that do not result in hospitalization; or development of drug dependency or drug abuse.

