7.5.8. Adverse Event Reporting

Investigator site reporting requirements for AEs are summarized in Table 6.

Table 6: Investigator Site Requirements for Reporting Adverse Events

Event	Recorded on the eCRF	Reported on the SAE/Pregnancy Report Form to PTC Pharmacovigilance Within 24 Hours of Awareness
Serious AE	All	All
Non-Serious AE	All	None
Exposure to the study drug during pregnancy or breastfeeding, and occupational exposure	All (regardless of whether associated with an AE), except occupational exposure	Exposure during pregnancy, exposure via breastfeeding, occupational exposure (regardless of whether associated with an AE)

Abbreviations: AE, adverse event; eCRF, electronic case report form; SAE, serious adverse event

All AEs should be followed up by the investigator until they are resolved, or the investigator assesses them as chronic or stable. The investigator should consider protocol guidelines and use his/her discretion in ordering additional tests as necessary to monitor the resolution of such events. In the event of additional investigations, the PTC Pharmacovigilance Department or designee should be informed via e-mail or fax. A subject withdrawn from the study because of an AE must be followed by the investigator until clinical recovery is complete and laboratory results have returned to normal, or until progression has been stabilized. Follow-up may need to continue after the subject has discontinued from the study, and additional investigations may be requested by the PTC medical monitoring team.

The first day of AE reporting will coincide with the date of signing of informed consent and including a minimum of 30 calendar days after the last administration of study drug.

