6.2. Adverse Events

The AE verbatim descriptions (investigator terms from the CRF) will be classified into medical terminology using the MedDRA. AEs will be coded by System Organ Class (SOC) and PT using MedDRA, Version 23.0 or later.

AE summaries will be presented by treatment for double-blind period, and by treatment sequence and overall for on-vatiquinone period, unless specified otherwise.

Only treatment-emergent AEs (TEAEs) will be included in summary tables. All AEs will be presented in subject data listings.

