6.2.1. Treatment Emergent Adverse Event

A TEAE is defined as an AE that had an onset date on or after the first dose of study drug but prior to 30 days after last dose or it occurs prior to first dose of study drug and worsens in severity after first dose of study drug.

AEs with missing or partial onset date and cannot be determined if it occurred prior to the first dose of study or which treatment period it occurred will be counted as TEAE under that treatment period.

A TEAE will be considered occurring during double-blind period if the AE had an onset date or date of worsening on or after the date of first dose of double-blind treatment and:

- Prior to the date of the first dose of open-label treatment if subject enrolled into open-label period
- Within 30 days of the date of the last dose of double-blind treatment if the subject does not enroll into open-label period

A TEAE will be considered occurring during the on-vatiquinone period if the AE had an onset date or date of worsening on or after the date of the first dose of vatiquinone treatment and within 30 days of the date of the last dose of vatiquinone treatment.

Overview TEAE table, including number and percentage of subjects with TEAEs, treatment related TEAE, treatment related serious TEAEs, TEAEs leading to study discontinuation, TEAEs by severity, and treatment related AE by severity will be provided.

Summary information (the number and percentage of subjects by treatment group or by treatment sequence, where appropriate) will be tabulated for:

- Incidence of TEAEs by SOC and PT
- Incidence of TEAEs by PT in descending order
- Incidence of treatment-related TEAEs by SOC and PT
- Incidence of TEAEs by SOC, PT, and maximum CTCAE grade
- Incidence of TEAEs by SOC, PT, and relationship to study drug

AE tables will be sorted by SOC and then PT in decreasing frequency of the number and percentage of subjects in the Vatiquinone group.

By-subject listing will be provided for AEs.

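### Possibly related events with late onset are recorded and listed, but the SAP's TEAE-only tables omit them without declaring it, and its 30-day cut-off is inconsistent

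*Protocol*

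**What the plan says.** **What is recorded.** Protocol 7.5.5 adds to the ordinary reporting duty "any known untoward event that occurs subsequent to the AE reporting period that the investigator assesses as possibly related" to the product. Protocol 7.5.2 makes the parallel provision for fatal events: "any AE resulting in death that occurs subsequent to the AE reporting period and that the investigator assesses as possibly related" to study drug is to be reported as serious. AE reporting starts at consent and runs on, "including a minimum of 30 calendar days after the last administration of study drug" (Protocol 7.5.8). SAE reporting runs through 30 days after the last dose (Protocol 7.5.9). The follow-up call "should be completed 30 days (± 7 days) post last study drug administration or termination visit, whichever is later" (Protocol 7.1.4).

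**What is declared as an endpoint.** Protocol 2.2.4.1 and SAP 1.3.4.1 both name "Drug-related SAEs" and drug-related AEs, with no onset window. Protocol 8.4.6.4 lists treatment-related AEs and SAEs for tabulation as items separate from TEAEs, without a treatment-emergent qualifier.

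**What is tabulated.** SAP 6.2 says "Only treatment-emergent AEs (TEAEs) will be included in summary tables"; its next sentence puts all AEs in subject listings. SAP 6.2.1 defines a TEAE chiefly by an "onset date on or after the first dose of study drug but prior to 30 days after last dose". Two other routes also count: a pre-dose AE that worsens after first dose, and an AE whose onset cannot be placed. The incidence tables of related AEs (SAP 6.2.1) and related SAEs (SAP 6.2.2) are limited to treatment-emergent events. SAP 6.2.2 adds listings of deaths, SAEs and AEs leading to discontinuation during the study. SAP 3.10 reports no major change in analysis from the protocol and does not mention this restriction.

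**The concern.** The protocol goes out of its way to collect events that begin after the reporting period when the investigator attributes them to study drug. It also says subjects will be watched for rebound after stopping (Protocol 7.1.4) and counts AEs resulting from withdrawal of study drug as reportable (Protocol 7.5.1). Post-treatment drug effects are thus anticipated, and the drug-related endpoints as worded would include them.

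The SAP's tables do not. A by-subject listing shows that an event happened, but it gives no incidence by arm, and the tables are where arms are compared. With about 30 subjects per arm, a single subject is 1/30 = 3.3% of an arm, so a rule that removes even one related SAE would be visible. That figure is the unit of the table, not an estimate of how many events would be lost.

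**Working it through.** There is no stated figure to reproduce. The check is a comparison of the rules and a day count, taking the date of last dose as day 0.

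**1. Last onset day under each rule**

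| Rule | Source | Last onset day |
|---|---|---|
| General TEAE definition (before 30 days) | SAP 6.2.1 | 29 |
| Double-blind TEAE, subject not entering extension (within 30 days) | SAP 6.2.1 | 30 |
| On-vatiquinone TEAE (within 30 days) | SAP 6.2.1 | 30 |
| SAE reporting (through 30 days) | Protocol 7.5.9 | 30 |
| AE reporting (a minimum) | Protocol 7.5.8 | at least 30 |
| Possibly related event | Protocol 7.5.5 | no limit |

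The two readings within SAP 6.2.1 differ by 30 − 29 = 1 day. An SAE that begins on day 30 is inside the protocol's reporting window and the SAP's period rules, but fails the general TEAE definition.

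**2. What the follow-up call can pick up.** The call falls between 30 − 7 = day 23 and 30 + 7 = day 37, or later if the termination visit comes after the last dose. A call on day 37 can record onsets that no table counts:

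- general rule: days 30 to 37, which is 37 − 30 + 1 = 8 days;
- period rules: days 31 to 37, which is 37 − 31 + 1 = 7 days.

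Possibly related events that become known after the call are recorded without time limit and are likewise not tabulated.

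**3. Tracing one event.** Take an SAE judged possibly related, with onset on day 35.

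- Protocol 7.5.5: recorded.
- Protocol 2.2.4.1 and 8.4.6.4: within the drug-related SAE endpoint and the planned tables as worded.
- SAP 6.2.1: not a TEAE.
- SAP 6.2 and 6.2.2: in no summary table; present in the all-AE listing and, if it counts as during the study, in the SAE listing.
- SAP 3.10: the difference from the protocol is not stated.

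**4. Who is affected.** For a subject who enters the extension, the double-blind count ends at the first open-label dose and later events move to the on-vatiquinone period (SAP 6.2.1). The post-dose cut-off therefore bears on the placebo-controlled comparison only through subjects who do not enter the extension. In the on-vatiquinone tables it applies to anyone who stops vatiquinone.

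**5. Fit with the SAP's own periods.** For non-continuing subjects, SAP 2.2.1 runs the double-blind period to the last study visit and uses it to summarise safety. SAP 2.2.2 runs the on-vatiquinone period to the end of the study. If that end falls more than 30 days after the last dose, a related event can lie inside the stated summary period and still be left out of the tables.

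**The case against.** The best defence is that recording and tabulating are different jobs. A fixed treatment-emergent window gives subjects a comparable period of ascertainment. Events after the follow-up call reach the sponsor only if someone happens to report them, and only if judged related. Mixing them into TEAE incidence would blend actively and passively collected data. All AEs are still listed, and deaths, SAEs and discontinuation events have their own listings. Protocol 7.5.6 ties a possible relationship to events coinciding with administration, so few late events may qualify. A separate open-label SAP, not among these documents, is also planned (SAP 1).

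Most of this stands. It is a good reason to keep the TEAE definition fixed and to show late related events separately. It does not explain why the tables are narrower than the endpoints and than Protocol 8.4.6.4 without a word in SAP 3.10, nor the one-day conflict.

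Three stronger readings are tempting and are not supported:

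- *Late events vanish from safety reporting.* They do not; they are missing from the summary tables only.
- *The comparison between arms is biased.* The cut-off is the same in both arms, and the documents give no rate of stopping by arm. Any imbalance is conjecture.
- *The loss can be sized from past experience.* Protocol 1.4.2 reports 7 possibly related SAEs in 5 subjects among over 500 treated. That is 5/500 = 1%, which suggests 0.01 × 30 = 0.3 subjects in an arm. This ignores exposure. Thirty subjects for 168 days is 5,040 patient-days against more than 523,000, and 5 × 5,040/523,000 ≈ 0.05, assuming a constant rate and full exposure. Even that covers related SAEs at any time, not late ones, so neither number measures this issue.

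**Conclusion.** The point holds as an undeclared mismatch. The protocol records possibly related events without an onset limit and plans tables of related AEs and SAEs on the same footing. The SAP tabulates only treatment-emergent ones and does not say it has narrowed the output. Late related events are listed but enter no by-arm incidence of the declared drug-related endpoints. Separately, SAP 6.2.1 contradicts itself by one day, and its general rule excludes a day-30 SAE that the protocol's reporting window includes.

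The effect is confined to descriptive safety output; no test, alpha or power is affected. The number of events involved cannot be derived from the documents and may be zero. The conclusion assumes that the general TEAE definition is read literally, with the last-dose date as day 0, and that the separate open-label SAP does not already supply the missing count for the on-vatiquinone period.

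**What to change.** 1. In SAP 6.2.1, keep a fixed TEAE window, but make the general definition run through 30 days after the last dose so that it agrees with the period rules and with Protocol 7.5.9.
2. Add a separate, flagged by-arm count of AEs and SAEs that the investigator assesses as possibly or probably related, regardless of onset date, attributed to the last treatment received. Leave the TEAE tables as they are.
3. State in SAP 3.10 that AE summary tables are limited to TEAEs, whereas Protocol 8.4.6.4 lists related AEs and SAEs without that limit.

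The cost is a wording change, one sentence in SAP 3.10, a flag in the AE dataset and a short table. The downside is small: collection after the follow-up call is passive, so the late counts should be labelled descriptive and not read as rates comparable with the TEAE incidences.

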7.5.6. Describing Adverse Event Relationship to Study Drug

The investigator should provide an assessment of the relationship of the AE to the study drug, ie, whether there is a reasonable possibility that the study drug caused the AE, using the considerations outlined in [Table 4](#).

Table 4: Relationship of Study Drug to Adverse Event Relationship

Relationship	Description
Probable	A clinical event in which a relationship to the study drug seems probable because of such factors as consistency with known effects of the drug; a clear temporal association with the use of the drug; improvement upon withdrawal of the drug; recurrence upon rechallenge with the drug; lack of alternative explanations for the event.
Possible	A clinical event occurring coincident with administration of the study drug and which may or may not be explained by concurrent disease or other drugs or chemicals. Information on drug withdrawal or rechallenge may be lacking.
Unlikely	A clinical event with a temporal relationship to the study drug exposure that does not preclude causality but for which there is a clear alternate cause that is more likely to have caused the AE than study drug. Such alternatives include a concomitantly administered drug, the subject's disease state, other medical conditions, or environmental factors.
Unrelated	A clinical event, for which a relationship to the study drug seems improbable because of factors such as inconsistency with known effects of the study drug, lack of a temporal association with study drug administration, lack of association of the event with study drug withdrawal or rechallenge, and/or presence of alternative explanations for the event. Alternative explanations might include a known relationship of the AE to a concomitant drug, medical history of a similar event, the subject's disease state, other medical conditions, or environmental factors.

Abbreviation: AE, adverse event

7.5.7. Grading of Severity of Adverse Event

The severity of AE will be graded using CTCAE Version 5.0 (refer to the Study Manual). For each episode, the highest severity grade attained should be reported.

If a CTCAE criterion does not exist, the investigator should use the grade or adjectives: Grade 1 (mild), Grade 2 (moderate), Grade 3 (severe), Grade 4 (life-threatening), or Grade 5 (fatal) to describe the maximum intensity of the AE. For purposes of consistency with the CTCAE, these intensity grades are defined in Table 5.

Table 5: Grading of Adverse Event Severity Grade

Grade	Adjective	Description
Grade 1	Mild	Sign or symptom is present, but it is easily tolerated, is not expected to have a clinically significant effect on the subject's overall health and well-being, does not interfere with the subject's usual function, and is not likely to require medical attention
Grade 2	Moderate	Sign or symptom causes interference with usual activity or affects clinical status, and may require medical intervention
Grade 3	Severe	Sign or symptom is incapacitating or significantly affects clinical status and likely requires medical intervention and/or close follow-up
Grade 4	Life-threatening	Sign or symptom results in a potential threat to life

Grade 5	Fatal	Sign or symptom results in death
---------	-------	----------------------------------

7.5.8. Adverse Event Reporting

Investigator site reporting requirements for AEs are summarized in Table 6.

Table 6: Investigator Site Requirements for Reporting Adverse Events

Event	Recorded on the eCRF	Reported on the SAE/Pregnancy Report Form to PTC Pharmacovigilance Within 24 Hours of Awareness
Serious AE	All	All
Non-Serious AE	All	None
Exposure to the study drug during pregnancy or breastfeeding, and occupational exposure	All (regardless of whether associated with an AE), except occupational exposure	Exposure during pregnancy, exposure via breastfeeding, occupational exposure (regardless of whether associated with an AE)

Abbreviations: AE, adverse event; eCRF, electronic case report form; SAE, serious adverse event

All AEs should be followed up by the investigator until they are resolved, or the investigator assesses them as chronic or stable. The investigator should consider protocol guidelines and use his/her discretion in ordering additional tests as necessary to monitor the resolution of such events. In the event of additional investigations, the PTC Pharmacovigilance Department or designee should be informed via e-mail or fax. A subject withdrawn from the study because of an AE must be followed by the investigator until clinical recovery is complete and laboratory results have returned to normal, or until progression has been stabilized. Follow-up may need to continue after the subject has discontinued from the study, and additional investigations may be requested by the PTC medical monitoring team.

The first day of AE reporting will coincide with the date of signing of informed consent and including a minimum of 30 calendar days after the last administration of study drug.

7.5.9. Serious Adverse Event Reporting

All SAEs occurring from the Screening Visit through 30 days following the last dose of study drug should be reported via the SAE report form to PTC within 24 hours of becoming aware of the event(s). In addition, the AE portion of the eCRF must also be completed.

The SAE report form should be signed by the investigator; however, if the investigator is unable to sign at the time of the event or within 24 hours, the form should be signed by the clinical staff member reporting the SAE (eg, the study coordinator). The SAE report form must be faxed or e-mailed to the PTC Pharmacovigilance Department or designee and to the site IRB/IEC (if required by local regulations) within 24 hours.

Follow-up information to the SAE should be clearly documented as “follow-up” in the SAE report form and must also be faxed or e-mailed to the same party. All follow-up SAE report forms for the event must be signed by the investigator. Any source documents (eg, progress notes, nurses’ notes, laboratory and diagnostic test results, discharge summaries) provided to the sponsor should be redacted so that the subject’s name, address, and other personal identity information are obscured. Only the subject’s study number and initials are to be provided (in regions where the provision of such information is permitted). The information in the AE portion of the eCRF and the SAE report form(s) must match or be reconciled. Where the same data are collected, the forms must be completed in a consistent manner. For example, the same AE term should be used on both forms.

In the rare event that the investigator does not become aware of the occurrence of an SAE immediately (for example, if a subject initially seeks treatment elsewhere), the investigator is to report the event within 24 hours after learning of it and to document his/her first awareness of the AE.

The PTC Pharmacovigilance Department contact information for reporting SAEs is provided below. This information is also provided in the Study Manual and in the SAE report form.

PTC Therapeutics Safety Department
Attention: Pharmacovigilance
E-mail: [contact]
[contact]

